**Visit 2: (1 Week post Restasis dispensing)**

- a. Update past medical history, past ocular history, allergies, medications
- b. Visual acuity assessments of both eyes (logMAR)
- c. Subject's evaluation of symptoms via OSDI
- d. Tolerability questionnaire
- e. Oculus Keratograph 5M R-Scan with lens (automatic classification of redness)
- f. Remove lens
- g. Oculus Keratograph 5M R-Scan without lens (automatic classification of redness)
- h. Slit lamp examination (without lens) including:
  - a. anterior segment and ocular surface
  - b. conjunctival redness (Efron Grading Scale, Modified Efron Grading Scale)
  - c. corneal staining with sodium fluorescein (NEI Grading System)
  - d. conjunctival staining with lissamine green (NEI Grading System)

**Visit 3: (4 Weeks post Restasis dispensing)**

- a. Update past medical history, past ocular history, allergies, medication
- b. Visual acuity assessments of both eyes (logMAR)
- c. Subject's evaluation of symptoms via OSDI
- d. Tolerability questionnaire
- e. Oculus Keratograph 5M R-Scan with lens (automatic classification of redness)
- f. Remove lens
- g. Oculus Keratograph 5M R-Scan without lens (automatic classification of redness)
- h. Slit lamp examination (without lens) including:
  - a. anterior segment and ocular surface
  - b. conjunctival redness (Efron Grading Scale, Modified Efron Grading Scale)
  - c. corneal staining with sodium fluorescein (NEI Grading System)

d. conjunctival staining with lissamine green (NEI Grading System)

## 9.0 Study Endpoints

The study endpoints to analyze safety, tolerability and efficacy are as follows:

- a) Visual Acuity (logMAR)
- b) Tolerability questionnaire
- c) Ocular Surface Disease Index (OSDI)
- d) Corneal staining with sodium fluorescein (NEI Grading System)
- e) Conjunctival staining with lissamine green (NEI Grading System)
- f) Conjunctival redness, Efron and modified Efron scale
- g) Oculus Keratograph 5M R-Scan value

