**[contact]**

**[[contact]](mailto:[contact])**

## **1.0 Objectives**

The goal of this prospective observational pilot study is to evaluate the tolerability and safety of RESTASIS (cyclosporine ophthalmic solution 0.05%) when added to the PROSE (Prosthetic Replacement of the Ocular Surface Ecosystem) lens reservoir in patients with ocular surface disease (OSD). Secondary endpoints include early (1-month) efficacy data for ocular signs and symptoms.

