## 10.0 Procedures Involved

The following table outlines each of the study visits and tells what procedures will be done at each visit:

Procedure	Length of Time Required for Participants
VISIT 1A: Initial Evaluation	
Informed consent & HIPAA	30 minutes
General History and medications	3 minutes
Visual Acuity	2 minutes
Tolerability Survey & OSDI	10 minutes
Slit-lamp Examination with assessment of PROSE devices	5 minutes
R-scan (pre and post PROSE removal)	10 minutes
Slit-lamp examination (after lens removal)	5 minutes
Instructions and dispensing product	10 minutes
TOTAL TIME	75 minutes

Procedure	Length of Time Required for Participants
VISIT 1B: Evaluation after 2 weeks with buffered saline	
General History and medications	3 minutes

Visual Acuity	2 minutes
Tolerability Survey & OSDI	10 minutes
Slit-lamp examination (after lens removal)	5 minutes
R-scan (pre and post PROSE removal)	10 minutes
Instructions and dispensing product	10 minutes
TOTAL TIME	40 minutes

Procedure	Length of Time Required for Participants
VISIT 2: Week 1 after dispense Restasis	
General History and medications	3 minutes
Visual Acuity	2 minutes
Tolerability Survey & OSDI	10 minutes
R-scan (pre and post PROSE removal)	10 minutes
Slit-lamp Examination (after lens removal)	10 minutes
TOTAL TIME	35 minutes

Procedure	Length of Time Required for Participants
VISIT 3: Week 4 after dispense Restasis	
General History and medications	3 minutes
Visual Acuity	2 minutes
Tolerability Survey & OSDI	10 minutes
R-scan (pre and post PROSE removal)	10 minutes
Slit-lamp Examination (after lens removal)	10 minutes
TOTAL TIME	35 minutes

Figure 1. Table including organization of examinations done at each study visit

Test	Description
General History and Medications	Participants will be asked questions about their general, ocular and medication use histories along with contact lens use history if applicable.
Lens Evaluation	The PROSE device fit and vision will be evaluated.
Visual Acuity	The participant's vision in each eye while wearing lenses will be measured with a high contrast visual acuity chart. The participant will be asked to cover one eye and read the chart, and this procedure will be repeated for the other eye.

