Slit-lamp Examination	The participant's front portion of each eye and contact lenses will be examined with a lighted microscope. The participant will be asked to place his/her chin on the chinrest and place his/her forehead against the bar and look straight ahead. The instrument's light will be shined onto the eye to visualize the ocular surface for approximately 2-3 minutes per eye.
Sodium Fluorescein/Lissamine Green	Sodium fluorescein/Lissamine Green staining will be used to evaluate ocular surface damage indicated by cell damage or death and for assessing an open vs closed PROSE device system. Corneal and conjunctival staining will be scored using the NEI Grading System.
R-Scan	Non-invasive imaging modality with automated classification of ocular redness level. Instrument used: OCULUS Keratograph 5M. The participant will be asked to place his/her chin on the chinrest and place his/her forehead against the bar and look straight ahead. The investigator will perform a scan of the eye to obtain an image of the front surface of the eye. The computer will then use an embedded software algorithm to quantify the level of redness on a scale from 0 to 4 in 0.1 increments.
Questionnaires	Subjects will be asked to fill out the following questionnaires: 
 
• Ocular Surface Disease Index (OSDI)
 
• Restasis Tolerability Questionnaire
 

*Figure 2. Table including descriptions of tests*

Statistical Analysis:

Subject data will be compared to their baseline status prior to initiating usage of the study drug. Subjects will be reevaluated at 1 week and 1 month visits and the data will be evaluated and compared to baseline. This is a small preliminary pilot study to evaluate tolerability of this treatment model utilizing Restasis. Given the small number of subjects and given our question of initial tolerability, the predominant nature of the results are observational and meant to provide an early means of addressing the question of tolerability.

The following data will be collected. They are all minimal to no risk.

- Visual acuity
  - Visual acuity will be measured on a Snellen chart and converted to logMAR values
- Tolerability survey
  - The Tolerability Questionnaire involves the subject answer a series of questions to assess their symptoms.
- Ocular Surface Disease Index (OSDI)

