### 13.0 Risks to Subjects / Evaluating, Monitoring and Reporting Adverse Events / Quality Assurance

This study overall represents a minimal risk to subjects.

Risk with PROSE devices are those that are already associated with wearing any form of contact lens. All contact lens wearers are at risk for developing an abrasion ('cut' on the eye) during lens application or removal as well as inflammatory and/or infectious complications during lens wear, but there is no hypothesized added risk of these occurrences by participating in this study.

Use of RESTASIS does introduce the risk of a hypersensitivity or toxic reaction to an active or inactive ingredient in RESTASIS which could result in corneal or conjunctival irritation, redness, and/or discomfort.

"In clinical trials the most common adverse reaction following the use of RESTASIS® was ocular burning (17%). Other reactions reported in 1% to 5% of patients included conjunctival hyperemia, discharge, epiphora, eye pain, foreign body sensation, pruritus, stinging, and visual disturbance (most often blurring)".

As with any study there may be unanticipated adverse reactions or outcomes.

If a subject experiences an adverse event during the duration of the study, they will be instructed to call the study coordinator who will communicate with the investigators to determine the best course of action. If the subject needs to be seen due to an adverse event, a study investigator will examine them and the customary procedure for management will be followed.

If an adverse event such as an abrasion occurs during a study visit, the condition will be treated as it is customarily, and the fees associated with treatment will be covered by the study.

Any adverse event will be treated and followed in keeping with standard medical and optometric practice. Subjects will be given 24-hour contact information for BostonSight providers and instructions to call if they develop new ocular or visual symptoms while participating in this study. All AEs will be evaluated and managed in an appropriate timeframe at an appropriate facility according to the medical judgment of a BostonSight doctor. All BostonSight patients enrolled in the study will have an ongoing relationship and follow-up with BostonSight for the duration of this study and as long as PROSE devices are being worn.

Any adverse effects or unforeseen events relating to the study will be reported directly to the Principal Investigator and to NEIRB.

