### **Adverse event reporting guidelines:**

All adverse events must be reported in the subject's source documents, and recorded on an Adverse Event Case Report Form regardless of whether or not they are considered to be related to the test article. The recording should be within 24 hours of the time that the AE came to the attention of the Investigator. For non-serious AE it is sufficient to enter the AE information into the CRF. The Clinical Research Coordinator will review the database on a regular basis.

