**Novel Use of Cyclosporine Ophthalmic Emulsion 0.05% in a PROSE Device**

**NCT#: NCT04918823**

**Version: 8/27/2024**

## Statistical Analysis

Statistical analysis was performed using Visual Studio Code (Microsoft Corp., Redmond WA) with python version 3.9.12. Subject data post-treatment was compared to their baseline data, collected prior to initiating use of the study drug. For Group A, the data collected at Visit 1A was considered to be their baseline data pre-intervention. For Group B, the data collected at Visit 1B was considered to be their baseline data (post-initiation of Purilens and pre-initiation of cyclosporine). The core algorithm used was based on statistical functions module `scipy.stats`. For univariate data analysis (before/after visits), paired t-test was performed since every patient received treatment. Paired t-test was conducted by `scipy.stats.ttest_rel` and <https://www.statskingdom.com/paired-t-test-calculator.html>. For bi-variate data, two-way ANOVA (Analysis of variance) was performed. Two-way ANOVA was conducted by `sm.stats.anova_lm(model)` function. The significance level was set to a P-value of  $\leq 0.05$  in all instances of analysis.

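### Adverse events are recorded but no summary of them is planned, and the completer-only analysis set removes subjects who stopped because of one

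*Protocol*

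**What the plan says.** Protocol section 1.0 sets the goal: to "evaluate the tolerability and safety of RESTASIS" when it is added to the PROSE reservoir. Efficacy at one month is secondary.

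Section 9.0 begins "The study endpoints to analyze safety, tolerability and efficacy are as follows" and lists seven items: acuity, the tolerability questionnaire, OSDI, corneal staining, conjunctival staining, graded redness and the R-Scan value. The data list under Statistical Analysis in section 10.0 repeats the same seven.

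Adverse events are handled in section 13.0. They must be "recorded on an Adverse Event Case Report Form regardless of whether or not they are considered to be related to the test article", together with the action taken, and discontinuation is one of the coded actions. On how events come to light, the section says: "If a subject experiences an adverse event during the duration of the study, they will be instructed to call the study coordinator".

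Visit 2 in section 8.0 includes "Update past medical history, past ocular history, allergies, medications", and Visits 1B and 3 have an equivalent item. Section 10.0 explains the history item: "Participants will be asked questions about their general, ocular and medication use histories". It describes the tolerability instrument only in general terms: "The Tolerability Questionnaire involves the subject answer a series of questions to assess their symptoms".

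On analysis, the SAP says: "For univariate data analysis (before/after visits), paired t-test was performed since every patient received treatment". It adds two-way ANOVA for bivariate data. Section 23.0 of the protocol names further families of hypothesis test. Section 5.0 uses the first 10 eligible completers. Section 15.0 allows withdrawal for an adverse event and then leaves withdrawn subjects out of the analysis.

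**The concern.** The most direct safety data are collected, but no analysis is assigned to them. The seven listed measures do carry safety information. They are scored only at baseline, week 1 and week 4, however, and are analysed as changes within subjects. A paired t-test on acuity or staining cannot say how many subjects had an event, how many events were judged related, or how many ended treatment.

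The completer rule makes this more than a missing table. The subject whose experience says most about safety is the one who stops because of an event, and that subject is left out by design. If someone later counted events on the planned analysis set, the count would tend to be too low. In a first look at tolerability and safety by a new route of delivery, the result could appear cleaner than what the treated subjects experienced.

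**Working it through.** **Step 1. Is an adverse-event summary planned anywhere?**
- Section 9.0: seven endpoints, no adverse events.
- Section 10.0, Statistical Analysis: the same seven, and evaluation is directed at the endpoints.
- Section 23.0: comparisons of baseline with later data; no event count.
- SAP: paired t-test and two-way ANOVA; no count, proportion, interval, listing or safety population.
- Section 13.0: recording and reporting duties only.

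No place in the documents turns the recorded events into a result.

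**Step 2. The plan's own recruitment figure.** Section 5.0 wants 10 completers at about 10% drop-out: 10 / (1 − 0.10) = 11.1, rounded up to 12. This matches the stated 12. With 12 recruited, 12 × 0.90 = 10.8 completers are expected. At exactly 10 completers, 12 − 10 = 2 subjects lie outside the analysed set.

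**Step 3. What the completer rule can hide.** Assume that all 12 recruited subjects use Restasis and that those who leave do so because of an adverse event. This is an illustration; the documents give no such count. Intervals are exact (Clopper-Pearson). For 0 of n the upper limit is 1 − 0.025^(1/n), so for n = 10 it is 1 − 0.025^(0.1) = 0.308. The events counted here are those that led to withdrawal.

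| Withdrawn for an event | Analysed set | Exact 95% interval | Treated set | Exact 95% interval |
|---|---|---|---|---|
| 1 | 0/10 | 0 to 30.8% | 1/12 = 8.3% | 0.2 to 38.5% |
| 2 | 0/10 | 0 to 30.8% | 2/12 = 16.7% | 2.1 to 48.4% |

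Two is the largest number of withdrawals from 12 that still leaves 10 completers. In both rows the analysed set shows zero because of how it is defined. The intervals overlap, so this is not a claim about statistical difference. What is lost is the count itself and the record of who stopped and why.

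**Step 4. Are events likely at this size?** Section 12.0 quotes 17% for ocular burning and 1% to 5% for other reactions. Those rates come from trials of Restasis and are only assumed to carry over to use in the reservoir. The chance of at least one affected subject is 1 − (1 − p)^n:

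| p | n = 10 | n = 12 |
|---|---|---|
| 0.17 | 84.5% | 89.3% |
| 0.05 | 40.1% | 46.0% |
| 0.01 | 9.6% | 11.4% |

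This shows that events are likely to occur. It does not show that they would be missed, since some of these reactions overlap with the questionnaire, acuity and redness measures.

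**Step 5. How are events found?** No visit list or time table contains an item for adverse events. The stated route for subjects is the telephone call. Visits 1B, 2 and 3 also include a history update, symptom questionnaires and a slit-lamp examination, each of which may bring an event out indirectly.

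**The case against.** The strongest reply is that this is a small, mainly observational pilot in which any rate would be imprecise (0/10 is compatible with up to 30.8%). All the data are already required on the form with the action taken, and several endpoints overlap with the expected reactions: symptoms with the questionnaire, blurring with acuity, hyperaemia with the redness scales. The imprecision is real and is why the summary should be descriptive. It does not justify omitting the summary or excluding subjects who stopped for an event.

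Four stronger readings are tempting, and the documents do not support them.
- A reader might infer that subjects are never asked about adverse events. The history update includes ocular history, and section 13.0 also provides for serious events that staff observe. Only the absence of an explicit enquiry can be stated.
- A reader might infer that a short-lived or single-subject reaction would be lost. The questionnaire's items and recall period are not given, so it may capture burning or stinging since the last visit.
- A reader might infer that the final report will contain no adverse-event rate. The plan specifies none, but one could still be tabulated from the forms.
- A reader might infer that events in Group B's two-week Purilens lead-in will be pooled with events on the drug. Nothing says so, and the SAP takes that group's baseline at Visit 1B. The plan is simply silent on how the two periods are separated for adverse events.

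**Conclusion.** The point holds for the planned analysis. Safety is part of the main goal, adverse events are recorded in full, and neither the endpoint list, the protocol's analysis text nor the SAP uses them. Because sections 5.0 and 15.0 limit the analysis to the first 10 completers, the safety result as written cannot show events that led to discontinuation. In the illustration, 1 or 2 such subjects among 12 treated (8.3% or 16.7%) become 0 of 10. That size assumes that all 12 recruited subjects use the drug and that the withdrawals are due to events. The structural conclusion needs neither assumption.

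The weakness in ascertainment is smaller: no explicit enquiry is scheduled, and the indirect routes cannot be judged fully without the questionnaire.

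**What to change.** In section 9.0 and the SAP, add a descriptive safety endpoint. It should give the number and percentage of subjects with any ocular adverse event, any related event, any serious event and any event causing discontinuation, each with an exact 95% interval, plus a per-subject listing.

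- Denominator: all subjects who used Restasis in the reservoir at least once.
- State that this summary is exempt from the completer rule in sections 5.0 and 15.0.
- Count events from first Restasis use and list Group B lead-in events separately.
- If visits are still to come, add one open adverse-event question at Visits 1B, 2 and 3. If they are complete, as the past tense of the SAP suggests, tabulate from the existing forms.

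The cost is wording in two documents, one table and one listing, and about one minute per visit if the question is added. Asking directly will probably raise the number of events recorded, which the report should mention.

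### Acuity and staining are listed for safety, but the SAP analyses before/after data only by comparing means, which can hide a large worsening in one to three of 10 subjects

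*Protocol*

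**What the plan says.** Protocol Section 1.0 makes the main goal to "evaluate the tolerability and safety of RESTASIS" in the PROSE reservoir. Efficacy comes second: "Secondary endpoints include early (1-month) efficacy data for ocular signs and symptoms".

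Protocol Section 9.0 opens with "The study endpoints to analyze safety, tolerability and efficacy are as follows" and lists acuity, the tolerability questionnaire, OSDI, corneal staining, conjunctival staining and two redness measures. It does not say which measure answers which question.

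The SAP states: "For univariate data analysis (before/after visits), paired t-test was performed since every patient received treatment". It adds: "For bi-variate data, two-way ANOVA (Analysis of variance) was performed". One significance level, 0.05, applies throughout. Protocol Section 23.0 names further methods (signed-rank tests, linear models, correlation, regression), all of them at group level.

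Neither document defines a worsening threshold for a single subject, a count of subjects who worsen, or a shift or worst-change table. Protocol Section 13.0 has every adverse event recorded on a case report form, but adverse events are not in the endpoint list and the SAP does not summarise them. Protocol Section 15.0 leaves withdrawn subjects out of the analysis, including those withdrawn for an adverse event.

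**The concern.** A mean change suits the efficacy question of whether subjects improve on average. The safety question is whether anyone is made materially worse. Harm from a drug held against the eye under a lens could plausibly appear as a large change in a few subjects, with little change or some gain in the others. A mean averages that pattern away, and the same large values inflate the SD on which the test depends.

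At stake is the study's main conclusion. The acuity and staining results could be reported as showing no significant change, or a mean improvement, while a subject has lost several lines or has had a clear rise in staining.

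**Working it through.** **Inputs from the documents.** The analysed number is 10, the first 10 eligible completers (Protocol Section 5.0). The recruitment figure reproduces: 10/(1 - 0.10) = 11.1, rounded up to 12. There is no power calculation to reproduce. The test is the paired t-test at P ≤ 0.05 (SAP), taken here as two-sided because no side is stated. Corneal staining runs from 0 to 15 per eye (Protocol Section 10.0).

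**Assumptions.** The change patterns and the noise SD are mine, since the documents give neither. Steps 1 to 3 take one value per subject. A positive logMAR change is a loss.

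**1. Equal losses, the rest unchanged.** If k of n subjects lose an amount L, the mean is kL/n and the SD is L × √[k(n-k)/(n(n-1))]. So t = mean/(SD/√n) = √[k(n-1)/(n-k)], and L cancels. For n=10 (9 df):

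| k | t | P |
|---|---|---|
| 1 | 1.00 | 0.34 |
| 2 | 1.50 | 0.17 |
| 3 | 1.96 | 0.08 |
| 4 | 2.45 | 0.037 |

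The signed-rank test in Protocol Section 23.0 does not help. With four equal losses and the zeros dropped, the exact P is 2 × (1/2)^4 = 0.125.

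**2. Losses offset by gains.** One subject loses 0.50 logMAR and nine gain 0.06: mean = (0.50 - 0.54)/10 = -0.004, SD 0.177, P=0.94. For corneal staining, one subject rises by 6 and nine fall by 2: mean = (6 - 18)/10 = -1.2, P=0.17, which reads as a trend towards benefit.

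**3. Noise added.** With a change SD of 0.10 logMAR and two harmed subjects, simulation gives significance in about 8%, 8%, 5% and 2% of studies for losses of 0.2, 0.3, 0.5 and 0.7. Detection falls as the harm grows, so this is not ordinary low power.

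**4. Unit of analysis.** Acuity and staining are taken in both eyes, and the SAP does not say whether the eye or the subject is the unit. If 20 eyes were entered as independent and four worsened equally, t = √(4 × 19/16) = 2.18 and P=0.042. Two subjects harmed in both eyes would then reach significance.

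**5. Withdrawals.** Suppose 10 completers each gain 0.10 and two subjects who each lost 0.40 withdraw. The analysed mean is -0.10. With all 12 it is (-1.00 + 0.80)/12 = -0.02.

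**6. What a count would show.** Exact (Clopper-Pearson) 95% limits: for 0 of 10 the upper limit is 1 - 0.025^(1/10) = 30.8%; for 2 of 10 the interval is 2.5% to 55.6%.

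**7. False flags from a count.** With no harm and a change SD of 0.10, the chance that a study of 10 flags at least one subject on acuity is:

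| Rule | Chance |
|---|---|
| One change per subject, beyond 0.2: 1 - 0.9772^10 | 21% |
| Worst of two eyes and two visits, beyond 0.2 | 48-57% |
| Worst of two eyes and two visits, beyond 0.3 | about 5% |
| Beyond 0.2 at both visits in the same eye | 7-8% |

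The last three rows are simulated, with a baseline shared within each eye and a between-eye noise correlation of 0 to 0.8. The 21% does not apply to a table that takes the worst of four changes.

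**The case against.** The strongest reply is that the protocol does not rest safety on a t-test. Section 10.0 calls the results mainly observational, Section 23.0 leaves the methods open, and Section 13.0 sets up separate recording of adverse events whatever their cause, with serious-event reporting. A reader might infer that the mean has to serve as the sole safety result, or that individual changes may not be reported. The documents support neither reading: individual reporting is unplanned, not forbidden. There are also two post-baseline visits, so the limitation is one type of summary and not a single number.

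A reader might also take four harmed subjects as a fixed limit of detection. It is not. It assumes one value per subject and no change in the others, and it shifts if eyes are the unit. The offsetting examples are constructed and do not predict these data.

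What remains is narrower but sound. No stated analysis of acuity or staining looks at individual worsening. Adverse-event recording does not fill the gap, because no acuity loss or staining rise is defined as an event, no event summary is planned, and withdrawn subjects are removed from the analysis.

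**Conclusion.** The point holds as a missing per-subject safety summary. As written, the plan can report no change or a mean gain while one to three of 10 subjects worsen badly. With one value per subject, equal losses and no change in the rest, P is 0.34, 0.17 and 0.08 for one, two and three subjects. That result needs no assumed loss size or SD, but it does need those three conditions. The examples with gains and with noise show that masking can happen. They do not show that it did, or how likely it is. The change is worth making because safety is part of the main goal and the data needed are already collected.

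**What to change.** Keep the mean change for the 1-month efficacy reading. For safety, add a descriptive table to the SAP with these features:

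- It covers every subject who received the study drug, including those who withdraw and any beyond the first 10 completers.
- For acuity, corneal staining and conjunctival staining, it shows each subject's change per eye at Week 1 and Week 4.
- It gives the number of subjects, not eyes, who worsen beyond a stated threshold, with an exact 95% CI.
- The investigators choose the thresholds. The SAP, dated 8/27/2024, is written in the past tense, so it should label any threshold set after the data were seen as post hoc.

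Base the safety statement on this table together with a tabulation of adverse events, and not on the t-test.

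The cost is SAP wording and one table from data already collected; withdrawn subjects contribute whatever visits they attended. The main downside is false flags. The threshold and the rule for combining eyes and visits should be chosen with the rates in step 7 in view, and the staining measures add further chances of a flag. With about 10 subjects the intervals will be wide, and a count of zero would not exclude a true rate of up to about 31%.
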